B. Innovation: (1) The emphasis on the addiction potential of LCCs within a polyuse context represents a new approach to the study of tobacco use in young adults. By explicitly addressing the relative reinforcing values of LCCs and cigarettes, the conditions under which substitutability occurs for this population can be studied in detail. (2) Use of behavioral economic methods to evaluate the addiction potential of LCCs relative to cigarettes is a methodological innovation. Current survey-based studies cannot address the relative addictive value of these products, or take into account the influence of flavorings. Laboratory methods to address these issues have been costly, and have not been able to adequately address the substitutability of LCCs for cigarettes. The CPT has several advantages over other methods including being relatively easy for participants to understand and researchers to implement, and not requiring costly and specialized equipment [62]. Moreover, it can be more sensitive to detecting changes in the relative reinforcing effects of a product than subjective measures [63], making it uniquely suited to study the effects of flavors in LCCs. (3) Advances in CPT methodology to study flavors can be applied to the study of other characteristics like nicotine content, and will inform future research and policymaking. As a new investigator, the results of the proposed research will enable me to write a follow-up R01 to investigate flavored vs. unflavored LCC addictive potential and the association with subsequent smoking behaviors measured in real-time. In addition, I can submit future R level applications to further modify the CPT to study other polytobacco use and other tobacco product characteristics that may contribute to polyuse.

Hypotheses, Aims and Objectives:

➤ Aims & Aim-Specific Hypotheses:

- Aim 1: To characterize the addictive potential of LCCs compared to cigarettes in dual users.
 - Hypothesis 1a: LCC demand elasticity will be higher and intensity lower than that of cigarettes, indicating less addictive potential of LCCs
 - Hypothesis 1b: The slope of the cross-price elasticity of LCCs and cigarettes will be positive and statistically significantly different from zero, indicating substitutability of LCCs as cigarette prices increase.

- Aim 2: To compare the addictive potential of preferred flavored vs. unflavored LCCs.

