- **Study design:** The study will employ a prospective, randomized cross-over design with 125 non-treatment-seeking young adult (18-34) dual users of cigarettes and LCCs. Using the original CPT and the CPT modified for LCCs, we will assess demand for cigarettes as cigarette price increases, demand for flavored and unflavored LCCs as prices for these products increase, and demand for flavored and unflavored LCCs as *cigarette* price increases across two study visits. Prior to each visit, participants will receive (in random order) their preferred flavor and unflavored LCCs to use at home to validate their responses on the CPT. Study visits will take place 7 to 10 days apart. This strategy has been used in our previous study of e-cigarettes and shown to be a sufficient time period to examine the impact of flavors on likeability of the product [64]. See **Figure 2**.

[figure not shown]

Figure 2. Randomized crossover study design

- **Sample size and justification:** We will enroll 125 non-treatment-seeking young adults (18-34) who are regular dual users of cigarettes and LCCs (see inclusion criteria for definition). Sample size calculation: No studies to date have investigated the main outcome for the proposed study: demand elasticity and intensity for flavored and unflavored LCCs, and cross-price elasticity of flavored and unflavored LCCs for cigarettes [65-68]. Published cross-price elasticities of LCCs for cigarettes range from 2.73 for little cigar sales [67] to 174.5 for cigarillo sales in exclusive, daily cigarette smokers [65]. Therefore, the sample size was calculated in G*Power 3 (94) using the standard medium effect size ($d=0.5$) for two independent means [69], in order to capture statistically significant differences by sex. With a sample size of 102, we can detect an effect size of 0.5 with 80% power and $\alpha=0.10$. In [name] pilot study with dual users [70], the attrition rate was 18%. Therefore, the final sample size of 125 participants will account for attrition.

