 - **Minnesota Tobacco Withdrawal Scale-Revised (MTWS-R)** (previously called the Minnesota Nicotine Withdrawal Scale): to measure the withdrawal effects of smoking cessation as an assessment of nicotine dependence [77].
 - **Questionnaire of Smoking Urges (QSU)-Brief:** to comprehensively assess craving using 10 items that measure their thoughts and feelings about cigarette craving [78, 79]. It has been adapted to additionally ask about LCC craving.

- **Respiratory Form and Adverse Events log:** Subjects will rate potential adverse effects (cough, throat irritation, rhinitis, and mouth irritation, which have been noted in studies of cigarette smokers. We will assess symptoms on a 4-point scale: 0=absent, 1=mild, 2=moderate and 3=severe. Other AEs will also be recorded and severity rated.
- **Cigarette Evaluation Scale (CES):** to assess the subjective rewarding and aversive effects of cigarette smoking [80]. It has been adapted to additionally ask about LCC smoking.
- **Liking Survey:** to assess participants' likes and dislikes for foods, physical activity, common experiences, and tobacco products using a gLMS scale.
- **Cigarette Purchase Task (CPT):** to collect hypothetical consumption of cigarettes at escalating prices to calculate the demand breakpoint, intensity, elasticity and cross-price elasticity, O_{\max} , and P_{\max} [52, 55]. This is a measure of addictive potential of a product.
- **Cigar Purchase Task:** adapted from the CPT to ask about consumption of LCCs.
- **Cross-Price Purchase Task:** to collect hypothetical consumption of LCCs at increasing cigarette [49]. This will help to determine the substitutability of LCCs for cigarettes when cigarettes are prohibitively expensive.

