Next, participants will be shown one brand of LCC in several flavors (i.e., fruit, dessert, and alcohol)—as well as plain tobacco (unflavored)—and allowed to handle and smell them. They will then be asked to choose their preferred flavor. It is assumed that participants will have little difficulty selecting their preferred flavor, given that they are regular dual users and will likely have smoked a variety of flavors in their lifetime. Participants who prefer the unflavored LCC will be asked for their second preferred flavor. Next, they will be randomized to receive either their preferred flavor or unflavored LCC using urn randomization to balance groups on menthol cigarette status and sex. Based on their baseline smoking rate calculated from the TLFB, the study staff will dispense a 1-week supply of LCCs. The study staff will ask the participants to smoke the study LCCs in place of their normal LCCs as much as they are able to, and to smoke the study LCCs unaltered (without marijuana). At the end of the visit, research staff will provide participants with their personal (single-user) iCO Smokerlyzer device and instruct them on how and when to use it.

One to two days before Visit 2, research staff will use Webex to do a video call with participants. The time will be pre-arranged at Visit 1 with reminders via phone, email, or text. Participants will need to use their webcam on their phone or computer for the call. During the video call, research staff will observe as participants use their iCO device to measure their CO level and email the results to the staff. Staff will confirm receipt of the email prior to ending the call. The video call will ensure that participants are using the device correctly and giving correct readings. Alternatively, the participants can choose to video record themselves using the iCO and emailing the results to the staff.

Approximately 7-10 days after Visit 1, participants will return for Visit 2. The day prior to the visit, staff will email the Qualtrics surveys to participants so that participants can do them online ahead of time if they want to. Study staff will initially meet participants outside to administer the

CO test, then proceed inside for the rest of the study visit. Participants will return unused Week 1 products that were provided by the study, and complete the following procedures:

- **SAL test:** to ensure capacity to complete study procedures (one re-test allowed)

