- **Urine drug toxicology test:** will be dropped from study if they test positive for illicit drugs (excluding marijuana). Participants who test positive will be asked if they would like to be re-tested. If they agree, their visit will be scheduled within the next 3-7 days. If they still test positive, they will be dropped. If they do not test positive, the study team will conduct the rest of Visit 2 procedures.
- **Urine pregnancy test for women:** will be dropped from study if they test positive
- **TLFB:** to measure cigarette, LCC, marijuana, and other tobacco product use since the last visit
- **Past 7 Day Smoking:** use of cigarettes, study assigned LCCs, and other brand of LCCs in past 7 days, and reasons for use of other brand
- **MTWS-R**
- **QSU-Brief**
- **Respiratory Form and other Adverse Effects log:** since the last visit
- **CES:** adapted to ask about the study-provided Week 1 LCCs
- **Tobacco Perceptions Questionnaire:** beliefs about the harmfulness, acceptability, and addictiveness of Week 1 LCCs, as well as self-efficacy to quit Week 1 LCCs (questions are adapted from those asked about own brand in Visit 1 Tobacco Use History Questionnaires).
- **CPT**
- **Cigar Purchase Task:** adapted to assess Week 1 LCCs
- **Cross-Price Purchase Task:** adapted to assess Week 1 LCCs within the context of cigarette prices.

Next, participants will crossover to receive the other LCC type for one week following the same procedures. The amount they are given will be based on their baseline smoking from the TLFB.

One to two days before Visit 3, research staff will again use Webex for a pre-arranged video call to observe participants using the iCO device, or arrange for the participant to email a video that shows them using the iCO device and emailing results to study staff. The same procedures will be followed as in the first video call.

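### Hypothesis 1a compares cigarettes with LCCs using two similar tasks whose order is neither stated nor counterbalanced; if the order is fixed, product cannot be separated from task position

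*Combined protocol and SAP*

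**What the plan says.** Hypothesis 1a (Hypotheses, Aims and Objectives) predicts that "LCC demand elasticity will be higher and intensity lower than that of cigarettes, indicating less addictive potential of LCCs". Every participant supplies both sides of this comparison.

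The Visit 1 list under Study Procedures gives three purchase tasks in this sequence:

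1. the Cigarette Purchase Task, "to collect hypothetical consumption of cigarettes at escalating prices to calculate the demand breakpoint, intensity, elasticity and cross-price elasticity" and related indices;
2. the Cigar Purchase Task, "adapted from the CPT to ask about consumption of LCCs";
3. the Cross-Price Purchase Task, "to collect hypothetical consumption of LCCs at increasing cigarette" prices.

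The Visit 2 list has the same sequence and ends with the cross-price task "adapted to assess Week 1 LCCs within the context of cigarette prices". Visit 3 uses the Visit 2 questionnaires, reworded for the Week 2 product.

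The only randomization described concerns the product: "participants will receive (in random order) their preferred flavor and unflavored LCCs". The data-analysis paragraph compares the demand indices across products. The covariates it names, for the cross-price model, are age, gender, race and menthol status. Task order is not mentioned.

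On mode of completion, the day before Visits 2 and 3 "staff will email the Qualtrics surveys to participants", who may complete them in advance. Paper forms are also allowed, and telephone administration is possible at Visit 3.

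**The concern.** The two tasks behind Hypothesis 1a are close copies: the same escalating-price format, applied to cigarettes and then to LCCs. Answers to the second could shift because of fatigue, a sense of money already spent, or the answers just given to the first. If the cigarette task always precedes the LCC task, any such shift falls wholly on the LCC side of the difference.

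More participants or more visits would not help, because each repetition carries the same shift. No covariate helps either, because position never varies separately from product. The randomization of flavored and unflavored LCCs protects Aim 2 but gives no protection to the cigarette-versus-LCC contrast.

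**Working it through.** **1. The plan's own figures.** For two independent means with d = 0.5 and two-sided alpha 0.10, the noncentral t gives power 0.799 with 50 per group and 0.806 with 51. The total is therefore 2 × 51 = 102, as stated. Allowing for 18% attrition, 102 / 0.82 = 124.4, rounded up to 125, also as stated. Nothing below changes these figures.

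**2. Aliasing.** Let D be the true LCC-minus-cigarette difference in an index and b an additive shift in whichever task comes second.

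- Cigarette task always first: observed mean difference = D + b.
- Cigar task always first: observed mean difference = D − b.
- In either case D and b cannot be estimated separately, at one visit or at three.
- Randomized 50:50: ½(D + b) + ½(D − b) = D.

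**3. Illustration of size.** The documents give no value for b or for the within-person correlation ρ, so both are assumed. The inputs are n = 102 completers (Sample size and justification) and equal SDs for the two tasks. The standard error of the paired difference, in SD units, is √(2(1 − ρ)/102):

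| ρ | SE |
|---|---|
| 0.3 | 0.117 |
| 0.5 | 0.099 |
| 0.7 | 0.077 |

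With D = 0, the chance of a significant result for one index comes from the noncentral t with 101 df and noncentrality b/SE. For ρ = 0.5:

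| Assumed b (SD) | b/SE | two-sided 0.10 | two-sided 0.05 |
|---|---|---|---|
| 0.1 | 1.01 | 26% | 17% |
| 0.2 | 2.02 | 64% | 52% |
| 0.3 | 3.03 | 91% | 85% |

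At b = 0.2 and two-sided 0.10, the rate is 52% for ρ = 0.3 and 83% for ρ = 0.7.

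**4. Price of counterbalancing.** If order is left out of the model, the alternating shift ±b adds b² to the variance of the difference. The relative increase is b² / (2(1 − ρ)). At b = 0.2:

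- ρ = 0.3: 0.04 / 1.4 = 2.9%
- ρ = 0.5: 0.04 / 1.0 = 4%
- ρ = 0.7: 0.04 / 0.6 = 6.7%

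For an assumed paired effect of 0.25 SD with ρ = 0.5, power falls from 80.6% to 79.2%. An order term recovers this loss.

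**5. What counterbalancing does not remove.** Suppose second answers are pulled toward first answers by a fraction w, and let L and C be the unpulled LCC and cigarette answers.

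- Cigarette first: [(1 − w)L + wC] − C = (1 − w)(L − C).
- Cigar first: L − [(1 − w)C + wL] = (1 − w)(L − C).

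The shrinkage is the same in both orders, so a 50:50 split leaves it in place. Comparing only first-answered tasks between order groups avoids it. With 51 per group the SE is √(2/51) = 0.198 SD, twice the paired SE at ρ = 0.5.

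**The case against.** **The lists may not be the sequence.** They are introduced as things participants will complete. Surveys can be done online the day before, ahead of tests that stand above them in the Visit 2 list. The actual order would be set in the survey build or the forms, and part of the document was removed from the public text. This stands. A reader might infer that Aim 1 is confounded as a matter of fact, but the documents support only the conditional statement. The recommendation survives, because any single fixed order has the same defect and an unrecorded, varying order could not be adjusted for.

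**The scope is narrow.** The sample-size paragraph describes the main outcome through flavored and unflavored LCC indices and cross-price elasticity, not the cigarette-versus-LCC contrast. The flavor contrast uses the same task at the same listed position in both periods, so a constant shift cancels. Hypothesis 1b concerns a slope within one task. This stands: only Hypothesis 1a is exposed.

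**The rejection rates restate an assumption.** They give the power of a t-test to detect an assumed bias, for one index. Hypothesis 1a needs elasticity higher and intensity lower. The rates therefore cannot be read as the chance that position alone would confirm it, and no direction is documented. They also do not describe anchoring, which creates no mean difference when none exists. All of this stands.

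**A constant order with the validated cigarette task first is defensible.** It keeps that task free of carry-over from the adaptation. But the LCC answers, which form the other half of the contrast, would remain exposed.

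**The cost may be larger than it looks.** The documents describe no randomizing function in the survey software, and paper and telephone modes need their own alternate versions. This stands, but the added work is modest.

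**Conclusion.** The point holds in conditional form. The available text neither fixes nor varies the order of the purchase tasks, and it neither records nor models that order. Under any one fixed order, the LCC-versus-cigarette difference in Hypothesis 1a cannot be separated from task position.

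The size of the problem is unknown. The range of 26% to 91% rests on assumed additive shifts of 0.1 to 0.3 SD, ρ = 0.5, 102 completers, a paired test at two-sided 0.10, a single index and no true difference.

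Two stronger inferences are not supported. One is that the trial's results are already biased, since neither the administration order nor any position effect is documented. The other is that counterbalancing would make the contrast free of bias, since it removes an additive position shift but not symmetric anchoring. Nor is this only a matter of documentation: writing down a cigarette-first order would complete the protocol and leave the aliasing in place.

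**What to change.** - At Visit 1, assign each participant 50:50 to complete either the Cigarette or the Cigar Purchase Task first.
- Keep that order for the participant at Visits 2 and 3, so that the flavored-versus-unflavored comparison is undisturbed.
- Keep the Cross-Price Purchase Task last.
- Prepare matching electronic, paper and telephone versions, and record the order used.
- Include task order as a term in the Aim 1 comparison.
- Report a first-task-only comparison between order groups as a less precise check for anchoring. It is cleanest at Visit 1, before participants have seen either task in the study.

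The cost is a second version of the forms, a minor amendment and one model term. If order is not modelled, the variance of the difference rises by about 3% to 7% at an assumed 0.2 SD shift. No extra visits or participants are needed, and 102 and 125 stand. Anyone measured before the change has a single order, so the Aim 1 result should also be shown for counterbalanced participants alone. The documents do not say how many those would be.

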- **All Recruitment Methods and Materials:** Participants will be recruited from the community using flyers, subject referral, newspaper ads, bus ads, radio ads, and online sources. Flyers (see attached) will be distributed at colleges, community centers, bars, and music venues in the communities in and near Farmington, Hartford, and Storrs. We will also run ads in the local buses and on local radio stations (see attached). Each radio ad runs for about 2 weeks, and each bus ad for about 4 weeks. We will also run ads in local newspapers, like the Yankee Flyer (see attached). Online sources, such as Facebook, Craigslist, and Google Ads, will also be used (see attached), and work especially well for recruiting young adults [81, 82]. We will also use these online ads for the UCHC Broadcast email. Lastly, we will ask participants to refer their friends to the study, and give them cards to distribute (see attached). All recruitment materials contain the study's phone number, website address to complete the screener, Google voice number to text, and email address. For participants who call, research staff will complete the screener over the phone. In addition to phone, interested individuals may also contact the study staff in response to recruitment materials by email or text. Study staff will contact individuals by phone, voice, and/or text to determine interest in participating in the study and, if interested, to refer them to the online screener or set up a phone call for screening. Recruitment will take place over 13 months, requiring enrollment of about 10 subjects per month. In [name] pilot study with young adult dual users, 63 participants were recruited in four months (~16 participants per month) using primarily Craigslist and subject referral. Therefore, the recruitment timeline is feasible. All recruitment procedures will be conducted by the PI ([name]), trained CRC research assistants, or trained UConn undergraduate student research assistants. Google voice will be used for texting only, and used from a secure device. It has been approved by IT security. A uhc email address has been obtained for the study, and will only be used from a secure device.

- Participants may receive reminder phone calls, text messages, and/or emails about upcoming appointments.
- ResearchMatch.com: Potential volunteers will be contacted by ResearchMatch with IRB-approved recruitment content for this study, not including direct study contact information such as study phone number. Volunteers will then have the option of replying 'yes' or 'no' through a set of quick links available in the recruitment message. If a volunteer chooses to respond in the affirmative, they will authorize ResearchMatch to release their contact information to the PI (or ResearchMatch designee) who will be responsible for managing that information according to institutional guidelines.

Consent Process:

- Process for Obtaining Consent (timing, location, length of discussion, time for consideration): Written informed consent will take place at Visit 1 at the CRC at UConn Health, at [name] lab at UConn Storrs, or in a private conference room at UConn Hartford. It will take place after a SAL analysis has verified the individual's capacity to complete study procedures. One re-test will be allowed. Study staff ([name], trained CRC research assistants, or trained UConn undergraduate student research assistants) will explain the study and administer consent. All participants will sign an IRB approved informed consent form. The form will explain what each participant can expect during the course of the study, potential risks and benefits, freedom to withdraw from the study at any time, and the procedure for pursuing a complaint against the institution. Study candidates will be advised that they will be free not to participate in this protocol, and if they elect to participate may withdraw at any time. Participants will be given all the time they want to ask questions about the study and decide whether or not they want to participate. The participants will also indicate on the consent form whether or not they want to be contacted for future research studies. After the participant gives informed consent, basic inclusion/exclusion criteria will be assessed. We expect the entire Visit 1, including consent, to take about two hours. It will take place in a private office.
- Who will Provide Consent (e.g. subject, legally authorized representative): The participant will provide written informed consent.
- Assessment of Capacity: Only participants who are able to provide consent will be enrolled. We will conduct SAL analysis to ensure study candidate is not incapacitated by alcohol.
- Requests for Waivers Consent: N/A

Budget / resources: Funding is being provided by the Patterson Trust Mentored Research Award for 2 years. \$95,000 total (\$50,000 in Year 1, and \$45,000 in Year 2). See attached funding agreement for the full budget.

Dissemination: Results will be disseminated via presentations at conferences sponsored by professional societies, such as the Society for Research on Nicotine and Tobacco (SRNT) Annual Meeting, as well as articles published in peer-reviewed journals.

Additional Information:

PROTECTION OF HUMAN SUBJECTS

A. Risks to Human Subjects

A1. Human Subjects Involvement, Characteristics, and Design. To achieve the three specific aims for the proposed research, human subjects will be recruited to complete survey instruments. The study does not involve any investigational new drugs or devices. The enrollment ceiling is 125 participants (approximately 50% women and 50% men) age 18-34 years of all ethnic and racial groups. At three study visits, participants will complete a series of surveys for data collection purposes. Urine pregnancy (for women), urine drug toxicology, and saliva alcohol level (SAL) screen tests will be conducted at Visit 1 to determine initial eligibility for the study. Urine pregnancy and drug toxicology tests will also be conducted at Visit 2 to determine continued eligibility, and SAL test will also be conducted at Visits 2 and 3 to ensure capacity to complete study procedures.

Inclusion Criteria (assessed at Visit 1):

1. Current regular dual user of little cigars/cigarillos (LCCs) and cigarettes, defined as: (a) report smoking cigarettes on ≥ 8 of the past 30 days, and (b) report smoking unaltered LCCs (without marijuana) on ≥ 8 of the past 30 days.
2. Able to speak, read and understand English
3. Age 18-34 years of age
4. Stable residence (not planning to move during study period)
5. Not intending to quit smoking cigarettes or LCCs within the next 2 weeks
6. Urinary cotinine level ≥ 100 ng/mL (one re-test will be allowed)

Exclusion Criteria (assessed at Visit 1 unless otherwise noted):

1. Pregnant for women (verified by urine pregnancy test at Visits 1 and 2)
2. Current use of nicotine replacement products or cessation products (e.g., bupropion) or intend to use within the next 2 weeks to minimize confounding effects of another product)
3. Positive alcohol screen (saliva alcohol level (SAL) ≥ 10 mg/dL; one re-test allowed; assessed at Visits 1, 2, and 3)
4. Illicit drug use other than marijuana (verified by positive drug toxicology test at Visits 1 and 2; one re-test allowed)
5. Met criteria for Cannabis Dependence assessed by the Cannabis Use Disorders Identification Test-Revised (CUDIT-R) (assessed during phone screening)

Participants from all racial/ethnic groups are eligible for this study if they meet the inclusion/exclusion criteria. The study sample will be drawn from this source population of young adults (18-34) because dual use of cigarettes and LCCs is most prevalent in this group. Efforts will be made to extend accrual to a representative population through community-based recruitment sampling. Recruitment strategies include local media advertisements (newspaper, bus, radio), flyers, subject referral, and online sources (Craigslist.com). To enhance retention, participants will be contacted up to 5 times to make the appointment for the study visit; if they are not responsive after 5 contacts, they will not be contacted anymore. Contacts will be made via email, phone, and/or text messaging, depending on participants' preferences. Participants will be approximately 50% women and 50% men in order to meet Specific Aim 3. Because this is a crossover trial, all participants will receive the same intervention. No

special vulnerable populations (such as fetuses, neonates, pregnant women, children, prisoners, and institutionalized individuals) will be involved.

A2. Sources of Materials. Research data will be obtained through questionnaires collected in-person via electronic or paper-based versions for the questionnaires. SAL, drug toxicology, and urine pregnancy tests will be collected solely for determination of eligibility and continued participation in the proposed study. Information on the specific instruments is provided in the Research Strategy section.

A3. Potential Risks. The potential risks from the study procedures include: (1) the risk of unauthorized disclosure of confidential material; (2) the burden of time to complete the research procedures; (3) exposure to potentially stressful circumstances; and (4) the risks of smoking. These issues are considered in the following paragraphs.

1) Risks of unauthorized disclosure of confidential material: Information about demographics, smoking history, current tobacco use, and risk perceptions will be collected about each participant. Data will be collected via paper forms and electronically, and stored electronically. There may be a small risk of unauthorized persons illegally accessing the data, but procedures will be in place to minimize this risk, including electronic data encryption and password protection, use of Qualtrics or REDCap for data management and storage (a secure cloud-based system), unique identifying codes and de-identification of the data, storage of hard copies of data in locked cabinets.

2) Burden of time to complete the research procedures: The procedures involved with data collection in this study require a moderate amount of time and multiple study visits.

3) Exposure to potentially stressful circumstances: Efforts to switch away from one's usual LCCs may be considered stressful by some participants.

4) Risks of smoking and toxicant exposure: Smoking is a significant risk factor for heart disease, cancer, respiratory disease, and many other health problems, and dual use may enhance those risks. Although we will choose a popular brand for the study-provided LCCs, they may not be the usual brand smoked by some participants. Because they vary in size and content, LCC brands vary in their levels of nicotine and toxicants. Therefore, the study-provided LCCs may increase some participants' nicotine and toxicant exposure compared to their usual brand.

B. Adequacy of Protection Against Risks

B1. Recruitment and Informed Consent. Community-based recruitment will take place using local media advertisements (newspaper, bus, radio), flyers, subject referral, and online sources (Craigslist.com). Participants will initially be screened over the phone. Those who are initially eligible will be scheduled for an in-person screening appointment (Visit 1). At Visit 1, potential participants will first provide a SAL to ensure they are able to take part in further procedures. If SAL \geq 10 mg/dL, one re-test will be allowed. If the individual still fails the SAL test, s/he will be deemed ineligible. If the SAL test is passed, potential participants will be given a thorough description of the study and asked to provide written informed consent. Next, basic inclusion/exclusion criteria will be assessed. Trained research staff or [name] will complete the consent procedures.

B2. Protections Against Risks.

1) Risks of unauthorized disclosure of confidential material: All research data will be coded to prevent identification of subjects. We will use a 5 digit study code (CRC study #) followed by a 3 digit number that reflects how many people enrolled in the study. The master list relating subject code numbers to their names will be kept separately in a locked file cabinet. Data generated during the course of this study will be de-identified (all identifiers removed and labeled within unique subject code). Paper copies of the data will be stored in a locked file cabinet. Electronic data will be encrypted, password protected, and kept on the secure Qualtrics or REDCap cloud-based data management software. Only the PI and research staff will have access to the master list.

2) Burden of time to complete the research procedures: Subjects will be compensated for the time spent participating in research assessments for this study. Every effort will be made to streamline the study visits. Study visits will be scheduled at the subject's convenience. Subjects will be free to refuse to complete any assessments at any time, and they may withdraw at any time.

3) Exposure to potentially stressful circumstances: We do not anticipate this issue will be significant because dual users often use more than one brand of LCC. However, subjects may withdraw at any time if they feel stressed from study participation.

4) Risks of smoking and toxicant exposure: To minimize this risk, only regular dual users of both cigarettes and LCCs (defined above) who are not interested in quitting will be eligible to participate, and participants may withdraw or stop study-provided LCC use at any time. When study-provided LCCs are dispensed by study staff at Visits 1 and 2, participants will also be given a sheet of paper with all seven of the warning labels that, starting on August 13, 2018, will be required to be on cigar packages by the FDA. At the end of Visit 3, we will advise participants that we do not endorse smoking and recommend cessation. We will ask if they would like cessation materials, and will provide materials as requested.

C. Potential Benefits of the Proposed Research to Human Subjects and Others

The risks entailed in this study are considered reasonable and minimal because the source population (from which the study sample will draw) are individuals who are currently using both cigarettes and LCCs and have no interest in quitting. There will be an additional burden of time to complete the research procedures, but we will take every effort to streamline the assessments. There are no direct benefits to subjects for participation. We believe that the small risks of the study are outweighed by the potential benefits of understanding the addictive potential of LCCs and how that addiction changes when flavor is eliminated. We expect that there will be societal benefits in understanding the addictive potential of flavored vs. unflavored LCCs in young adult dual users, which will be useful for cessation programs and regulatory purposes.

D. Importance of Knowledge to be Gained

Smoking is one of the leading health problems in the U.S. The burden of multiple tobacco product and LCC use is growing, particularly in young adults. Our understanding of the addictive potential of LCCs, and the moderating effects of flavor and sex, is limited at this time. By providing information about their addictive potential, we expect to inform cessation efforts targeting young adult dual users and regulatory decision-making on LCCs for prevention and cessation.

DATA AND SAFETY MONITORING PLAN

[name] will assume primary responsibility for safety of this study, executing the data and safety monitoring plan (DSMP), and complying with reporting requirements, under the mentorship of Drs. [name], and [name]. Because the study is low-risk and single-site, there will not be a Data and Safety Monitoring Board. [name] will meet with the study personnel on a weekly basis, and will be available at any time to identify and solve problems in the study's implementation, and provide advice on any adverse events experienced by participants during the study. The research assistant will be responsible for the monitoring of participants and will report to [name] as needed.

A. Safety Monitoring

The proposed study poses low risk of harm to participants; therefore, we expect that SAEs will be rare and not related to study participation. We will collect all respiratory and other AEs on log forms (see attached) and in a tracking database. Each AE will be graded (mild, moderate or severe). SAEs will be also noted. Additionally, we will note probable cause (unrelated, possibly related, or definitely related to the study). AEs and SAEs, even those clearly unrelated to the study such as accident or illness, will also be reported to [name] and either Drs. [name], or [name] (who are MDs). Any concerning events that could be related will be reviewed on an ongoing basis at study meetings. [name] and either Drs. [name], or [name] will determine how to proceed in consultation with Drs. [name] and [name] as needed.

Participants who experience any of the following will be said to have experienced an SAE, as defined by the FDA:

- Death
- Suicide or homicide attempt
- Persistent, serious suicidal or homicidal ideation, with intent and plan
- Congenital Abnormality or permanent disability
- Life-threatening events
- Overnight hospitalization (excluding planned surgeries or other planned procedures)

Any participant who experiences an AE or SAE will be assessed for causality, and referred to treatment if necessary. Any participant who experiences an SAE will be advised regarding options to continue or terminate participation in the study. All AEs will be reported to the IRB on an annual basis. All SAEs will be reported to the IRB of record within the required time limits.

B. Data Monitoring

[name] will assume primary responsibility for data accuracy and protocol compliance. Data will be collected securely electronically and double-checked by research staff. Audits of randomly selected participant files will be conducted quarterly to check on accuracy of data entry and protocol adherence. Adherence to protocols will also be ensured by ongoing supervision by [name], who will report regularly to Drs [name], and [name] in their regularly scheduled mentorship meetings. Protocol deviations as a result of staff error will be reported to the IRB with a protocol deviation report form. The protocol deviation report will outline the root cause of the problem and establish a plan of

